## 9.2 SAMPLE SIZE DETERMINATION

A total of 100 participants will provide at least 90% power to detect a 15% difference in the percentage of time participants spend in deep and REM sleep, as quantified using the Whoop sleep-tracking device after the four-week treatment phase. The CRO 83Bar will recruit 8,000 potential study participants using social media, will screen approximately 800 study participants via online screening surveys, will contact 440 participants from a call center, and will ultimately enroll 150 qualified study participants. Based on our two previous clinical studies with Defined CBD, we anticipate a maximum dropout rate of 33% in Le Rêve 3.0.

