### 9.4.2 ANALYSIS OF THE PRIMARY EFFICACY ENDPOINT(S)

The primary endpoint that will be analyzed in Le Rêve 3.0 is the percentage of time study participants spend in deep and REM sleep as quantified using wrist-worn sleep-tracking device Whoop. The difference in the mean percentage of sleep spent in deep and REM sleep in participants that received Defined CBD and the placebo control at the end of the two four-week treatment phases will be compared using a 2-sided test with an alpha level at 0.05 to evaluate superiority. The p-value and 95% confidence interval for the estimate of treatment difference in percentages will be estimated and constructed using the above-mentioned method.

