### 9.4.7 SUB-GROUP ANALYSES

Demographic measurements will be summarized using standard descriptive methods by cohort and treatment. Demographic summaries may include sex, race/ethnicity, and age.

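### Sections 9.1 to 9.4.3, read literally, compare only people with data from both phases, and with no efficacy set defined up to about 50 of the 150 enrolled can be left out.

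*Combined protocol and SAP*

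**What the plan says.** Section 9.2 states that "A total of 100 participants will provide at least 90% power to detect a 15% difference" in the share of deep and REM sleep. The same section says that the contract research organisation "will ultimately enroll 150 qualified study participants", and adds that "we anticipate a maximum dropout rate of 33" per cent.

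The primary analysis in section 9.4.2 compares mean percentages "in participants that received Defined CBD and the placebo control at the end of the two four-week treatment phases". Sections 9.1, 9.4.1 and 9.4.3 describe the comparison in nearly the same words.

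Section 9.3 is headed as the place for analysis populations. For efficacy it gives only the timing of the analysis. The one set defined by who is in it is the safety set, which section 9.4.4 describes as everyone randomised or enrolled who took any dose. Section 9 names no intention-to-treat set, missing-data method, model that uses one-period data, or sensitivity analysis.

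Under section 7.2, dosed participants who leave are not replaced, and the investigator may withdraw people for marked non-compliance. Section 9.4.5 marks baseline descriptive statistics as not applicable. Section 9.4.7 has demographics "summarized using standard descriptive methods by cohort and treatment".

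**The concern.** In a two-period crossover, the simple within-person contrast needs an outcome under both products. Anyone who leaves before giving usable second-period data drops out of that contrast, and leaving happens after treatment has begun. If it is related to response or tolerability, the completers are a selected group and their effect need not be the effect in the people who were randomised. The plan itself allows for losing a third of its enrolment, so the choice of analysis set could matter. As written, that choice is left to whoever analyses the data, and the nearest reading of the text is a completer analysis.

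The planned tables would not reveal a problem. With baseline statistics omitted and demographics split by treatment, completers appear under both products. Unless the undefined word cohort was meant as sequence, the split shows neither imbalance between sequences nor how leavers differ from those who stay.

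**Working it through.** **Step 1. Reproduce the plan's enrolment figure.** The inputs are all from section 9.2: 100 participants needed, maximum dropout 33%, 150 enrolled.
- 100 / (1 − 0.33) = 149.3, rounded up to 150. This matches the plan.
- In reverse, 150 × 0.67 = 100.5 remain and 150 × 0.33 = 49.5 are lost.

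Dropout is therefore covered by over-enrolment, and the 100 are those expected to remain. The 90% power cannot be checked, because no standard deviation or within-person correlation is given.

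**Step 2. Fix the denominator.** The 33% is set against the 150 enrolled. The schedule of activities (section 1.3) places randomisation at the start of Treatment 1, after two baseline weeks, while section 6.3 says only that it follows enrolment. Some of the 49.5 may leave before randomisation, so about 50 is an upper figure for people enrolled.

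**Step 3. How far could the two effects differ?** Assume 100 completers with mean effect D and 50 leavers with mean effect f × D. The effect in everyone is D × (100 + 50f) / 150.

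| f (assumed) | Effect in everyone | Completer estimate ÷ effect in everyone |
|---|---|---|
| 0 | 0.67 D | 1.5 |
| 0.5 | 0.83 D | 1.2 |
| 1 | 1.00 D | 1.0 |

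Nothing in the documents fixes f.

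**Step 4. What would a mixed model do under f = 0?** Assume equal variances (set to 1), within-person correlation ρ, 50 completers per sequence, and 50 leavers who give period 1 only, 25 on each product.

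With treatment and period as fixed effects and participant as random effect:
- Variance of the treatment effect from completers: 2(1 − ρ)/100.
- Variance from one-period participants: 1/25 + 1/25 = 2/25.
- Ratio of the two: (1 − ρ)/4.
- Expected estimate with inverse-variance weights: D / [1 + (1 − ρ)/4].

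With sequence added as a fixed effect, the four sequence-by-period means are fitted freely:
- Active-first sequence: the period 1 mean is (50/75)D = 2D/3, and the period 2 mean is shifted by −ρD/3. The difference is (2 + ρ)D/3.
- Placebo-first sequence: the difference is −D.
- Half the difference between sequences: (5 + ρ)D/6.

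| ρ (assumed) | Without sequence | With sequence |
|---|---|---|
| 0.3 | 1/1.175 = 0.85 D | 5.3/6 = 0.88 D |
| 0.5 | 1/1.125 = 0.89 D | 5.5/6 = 0.92 D |
| 0.7 | 1/1.075 = 0.93 D | 5.7/6 = 0.95 D |
| 0.9 | 1/1.025 = 0.98 D | 5.9/6 = 0.98 D |

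The same factors give the variance relative to the completer analysis: about 2% to 15% lower without sequence, and about 2% to 12% lower with it. A direct generalised least squares calculation gives the same values. Neither model reaches 0.67 D. Only an analysis that imposes zero effect on leavers does.

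**The case against.** The strongest reply is that the plan is silent and has not chosen a completer analysis. No completers-only rule is stated. The phrase about participants who received both products may only label the two conditions, since section 9.1 goes on to speak of two treatment groups, and the reference to the end of the phases may be a time point. Sizing on the number expected after dropout is routine and does not settle who is analysed. All of this stands, so the point is that people can be left out, not that the plan says they will be.

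Three stronger readings are tempting, and the documents support none of them:
- **That the plan specifies an as-received analysis.** No rule reassigns anyone by product actually taken, and section 6.2.2 describes packs already labelled Treatment 1 and Treatment 2.
- **That a third of those randomised are lost.** The 33% is a maximum, set against enrolment.
- **That the completer estimate overstates benefit.** In a blinded crossover, someone who leaves during a placebo-first period for lack of benefit says nothing about their response to the active product, and losing would-be responders biases the other way. Section 10.1.8 lists reasons for lost data unrelated to efficacy, such as a flat battery or a device not worn.

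It is also fair to say that reasons for withdrawal are recorded (section 7.2), so some information on leavers will exist, and that cohort in section 9.4.7 is undefined and could mean sequence. What remains is that no efficacy set or missing-data method is stated and that no planned table is split by completion status.

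**Conclusion.** The concern holds in a limited form. Taken literally, the efficacy sections give a contrast in people with data from both phases, and nothing in section 9 brings the others back. At the plan's own maximum dropout, up to about 50 of the 150 enrolled fall outside it.

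The direction and size of any bias cannot be derived from the documents. The factor of 1.5 is the extreme of an illustration, in which dropout is at its maximum and every leaver has zero effect. At half the completers' effect the factor is 1.2, and at the full effect there is no discrepancy.

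A mixed model is a better primary analysis because it keeps the one-period data. It is not a correction for selective dropout: under the zero-effect case it moves the estimate only to about 0.85 to 0.98 of the completer value at assumed correlations of 0.3 to 0.9 (0.88 to 0.98 with sequence fitted). The change should be made before unblinding. It does not by itself call the design into question.

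**What to change.** - **Section 9.3:** define the primary efficacy set as all randomised participants with at least one usable device night in either treatment period, analysed by the product assigned to that period. This is a modified set, because someone randomised who gives no usable treatment night stays outside it. Report how many there are.
- **Section 9.4.2:** name a mixed model with treatment, period and sequence as fixed effects and participant as random effect, keeping participants with one period only.
- **Sensitivity analyses:** report the completer result, and one analysis that varies the effect in leavers from the completers' value down to zero.
- **Section 9.4.7:** summarise demographics by randomised sequence and by completion status.

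The cost is plan wording, a little more analysis and some extra tables, all from data already to be collected. The gain in precision is modest, at about 2% to 15% lower variance under the assumptions above (2% to 12% with sequence fitted). The reported estimate may be smaller than a completer analysis would give.

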### 9.4.3 ANALYSIS OF THE SECONDARY ENDPOINT(S)

The difference secondary endpoints (total sleep time, sleep latency, the number of sleep disturbances, time spent in each sleep stage, percentage of time spent in each sleep stage, and subjective measures of sleep physiology as collected via participant surveys) in participants that received Defined CBD and the placebo control at the end of the two four-week treatment phases will be compared using a 2-sided test with an alpha level at 0.05 to evaluate superiority. The p-value and 95% confidence interval for the estimate of treatment difference in percentages will be estimated and constructed using the above-mentioned method.

### 9.4.4 SAFETY ANALYSES

The primary analysis set for safety analyses is defined as safety analysis dataset, which includes all participants who are randomized/enrolled and receive any dose of study treatment. All data collected during the study will be included in the safety summaries.

### 9.4.5 BASELINE DESCRIPTIVE STATISTICS

Not applicable.

### 9.4.6 PLANNED INTERIM ANALYSES

Not applicable.

### 9.4.7 SUB-GROUP ANALYSES

Demographic measurements will be summarized using standard descriptive methods by cohort and treatment. Demographic summaries may include sex, race/ethnicity, and age.

#### 9.4.8 TABULATION OF INDIVIDUAL PARTICIPANT DATA

Not applicable.

#### 9.4.9 EXPLORATORY ANALYSES

Not applicable.

### 10 SUPPORTING DOCUMENTATION AND OPERATIONAL CONSIDERATIONS

#### 10.1 REGULATORY, ETHICAL, AND STUDY OVERSIGHT CONSIDERATIONS

##### 10.1.1 INFORMED CONSENT PROCESS

###### 10.1.1.1 CONSENT/ASSENT AND OTHER INFORMATIONAL DOCUMENTS PROVIDED TO PARTICIPANTS

An informed consent form describing in detail the study intervention, study procedures, and risks will be given to study participants and written documentation of informed consent will be required prior to initiating Le Rêve 3.0. The informed consent to be used in Le Rêve 3.0 is submitted with this protocol.

###### 10.1.1.2 CONSENT PROCEDURES AND DOCUMENTATION

Informed consent is a process that is initiated prior to the individual's agreeing to participate in the study and continues throughout the individual's study participation. Consent forms will be IRB-approved and the participant will be asked to read and review the document. A member of the CBD Sleep Study Team will explain the research study to the participant and answer any questions that may arise. A verbal explanation will be provided in terms suited to the participant's comprehension of the purposes, procedures, and potential risks of the study and of their rights as research participants. Participants will have the opportunity to carefully review the consent form and ask questions prior to signing. The participants should have the opportunity to discuss the study with their family or surrogates or think about it prior to agreeing to participate. The participant will sign the informed consent document prior to initiating the study. Participants must be informed that participation is voluntary and that they may withdraw from the study at any time, without prejudice. A copy of the informed consent document will be given to the participants for their records. The informed consent process will be conducted and documented in the source document (including the date), and the form signed, before the participant initiates the study. The rights and welfare of the participants will be protected by emphasizing to them that the quality of their medical care will not be adversely affected if they decline to participate in this study.

###### 10.1.2 STUDY DISCONTINUATION AND CLOSURE

This study may be temporarily suspended or prematurely terminated if there is sufficient reasonable cause. Written notification, documenting the reason for study suspension or termination, will be provided by the suspending or terminating party to study participants and IRB. If the study is prematurely terminated or suspended, the PI will promptly inform study participants and IRB, and will provide the reason(s) for the termination or suspension. Study participants will be contacted, as applicable. Study may resume once concerns about safety, protocol compliance, and data quality are addressed, and satisfy the sponsor and IRB.

Circumstances that may warrant termination or suspension include, but are not limited to:

- Determination of unexpected, significant, or unacceptable risk to participants
- Insufficient compliance to protocol requirements
- Data that are not sufficiently complete and/or evaluable

#### 10.1.3 CONFIDENTIALITY AND PRIVACY

The investigator must assure that the participants' anonymity will be strictly maintained and that their identities are protected from unauthorized parties. Only an identification code will be recorded on any data form used in Le Rêve 3.0. Therefore, the study protocol, documentation, data, and all other information generated will be held in strict confidence. No information concerning the study or the data will be released to any unauthorized third party without prior written approval of the sponsor.

The study participant's contact information will be securely stored for internal use during the study. At the end of the study, all records will continue to be kept in a secure location for as long a period as dictated by the reviewing IRB or sponsor requirements.

Study participant research data, which is for purposes of statistical analysis and scientific reporting, will be transmitted to and stored at Defined Research. This will not include the participant's contact or identifying information. Rather, individual participants and their research data will be identified by a unique study identification number. The study data entry and study management systems used by Defined Research's staff will be secured and password protected. At the end of the study, all study databases will be de-identified and archived at Defined Research.

#### 10.1.4 FUTURE USE OF DATA

Data collected for this study will be analyzed and stored at Defined Research.

#### 10.1.6 SAFETY OVERSIGHT

Safety oversight will be under the direction of an independent safety monitor (ISM) named [name]. [name] has extensive experience and knowledge with National and International Drug Safety and Pharmacovigilance principles and Regulations (US FDA, EMA, MHRA, MHLW) and Clinical Trials design and development process. The ISM will provide input to Defined Research and the IRB as necessary.

#### 10.1.7 CLINICAL MONITORING

Clinical monitoring will be conducted to ensure that the rights and well-being of trial participants are protected, that the reported trial data are accurate, complete, and verifiable, and that the conduct of the trial is in compliance with the currently approved protocol/amendment(s), with International Conference on Harmonisation Good Clinical Practice (ICH GCP), and with applicable regulatory requirement(s).

- Members of the CBD Sleep Study Team will oversee clinical monitoring via daily text (SMS) messages with study participants to ensure compliance and to capture any AEs and SAEs.
- Members of the CBD Sleep Study Team will oversee clinical monitoring by ensuring that sleep-tracking data is being collected on a daily basis throughout the study.

#### 10.1.8 QUALITY ASSURANCE AND QUALITY CONTROL

Le Rêve 3.0 will be conducted in a decentralized manner. All data will be collected electronically via the cloud. Quality control (QC) procedures by the CBD Sleep Study Team will be implemented to ensure that sleep physiology data is being collected appropriately. Data QC checks will be run on a daily basis. If a study participant becomes noncompliant resulting in a lack of sleep physiology data being collected (for example, if the battery on their sleep tracking device runs out of charge; if the participant forgets to wear the sleep tracking device at night; or if the participant forget to connect the sleep-tracking device to their smartphone via Bluetooth), then the lack of data collection will automatically trigger the activation of a text (SMS) based application to communicate directly with that participant to help them resolve the lack of compliance issue. In the event the text-based notification system does not resolve the lack of compliance issue, a member of the CBD Sleep Study Team may also reach out to the study participant by phone or email to help resolve the issues.

#### 10.1.9 DATA HANDLING AND RECORD KEEPING

##### 10.1.9.1 DATA COLLECTION AND MANAGEMENT RESPONSIBILITIES

As stated above, all of the data that will be collected in Le Rêve 3.0 will be electronic and captured via the cloud. The investigator and CBD Sleep Study Team are responsible for ensuring the accuracy, completeness, legibility, and timeliness of the data reported. Clinical data will be collected by a 21 CFR Part 11-compliant data capture system provided by Whoop. The data system includes password protection and internal quality checks, such as automatic range checks, to identify data that appear inconsistent, incomplete, or inaccurate.

##### 10.1.9.2 STUDY RECORDS RETENTION

Study documents will be retained for a minimum of 2 years after completion of Le Rêve 3.0.

---

#### 10.1.10 PROTOCOL DEVIATIONS

A protocol deviation is any noncompliance with the clinical trial protocol or International Conference on Harmonisation Good Clinical Practice (ICH GCP). The noncompliance may be either on the part of the participant or the investigator. As a result of deviations, corrective actions are to be developed by the CBD Sleep Study Team and implemented promptly.

These practices are consistent with ICH GCP:

- 4.5 Compliance with Protocol, sections 4.5.1, 4.5.2, and 4.5.3
- 5.1 Quality Assurance and Quality Control, section 5.1.1
- 5.20 Noncompliance, sections 5.20.1, and 5.20.2.

It is the responsibility of the CBD Sleep Study Team to use continuous vigilance to identify and report deviations within one working day of identification of the protocol deviation. All deviations must be addressed in study source documents.

---

#### 10.1.11 PUBLICATION AND DATA SHARING POLICY

Data from Le Rêve 3.0 will be included a manuscript that Defined Research will submit for publication in a peer reviewed scientific journal. In addition, this trial will be registered at ClinicalTrials.gov, and results information from this trial will be submitted to ClinicalTrials.gov. Data from this study may be requested from other researchers three years after the completion of the primary endpoint by contacting Defined Research.

---

#### 10.1.12 CONFLICT OF INTEREST POLICY

Any actual conflict of interest of persons who have a role in the design, conduct, analysis, publication, or any aspect of this trial will be disclosed and managed, including in a scientific publication that may arise from Le Rêve 3.0. The study leadership has established policies and procedures for all study group members to disclose all conflicts of interest and will establish a mechanism for the management of all reported dualities of interest.

### 10.2 ADDITIONAL CONSIDERATIONS

Not applicable.

### 10.3 ABBREVIATIONS

AE	Adverse Event
CFR	Code of Federal Regulations
DHHS	Department of Health and Human Services
DRE	Disease-Related Event
eCRF	Electronic Case Report Forms
FDA	Food and Drug Administration
FDAAA	Food and Drug Administration Amendments Act of 2007
GCP	Good Clinical Practice
GLP	Good Laboratory Practices
GMP	Good Manufacturing Practices
HIPAA	Health Insurance Portability and Accountability Act
ICH	International Conference on Harmonisation
ICMJE	International Committee of Medical Journal Editors
IND	Investigational New Drug Application
IRB	Institutional Review Board
ISM	Independent Safety Monitor
ISO	International Organization for Standardization
NCT	National Clinical Trial
NIH	National Institutes of Health
NIH IC	NIH Institute or Center
OHRP	Office for Human Research Protections
PI	Principal Investigator
QA	Quality Assurance
QC	Quality Control
SAE	Serious Adverse Event
SAP	Statistical Analysis Plan
US	United States

#### 10.4 PROTOCOL AMENDMENT HISTORY

Version	Date	Description of Change	Brief Rationale

